Aim 1: Validate the Marijuana Purchase Task (MPT) measure via administration to a representative sample of marijuana users and assessment of smoking behavior in the laboratory (*n*=85). Hypothetical MPT responses (e.g., how many hits of marijuana would you take if they cost \$0.25?, \$0.50?, etc...) will be compared to responses on an Actual MPT whereby one of the subject's response choices is selected at random to determine the amount of marijuana to be administered. Marijuana smoking topography will be assessed during a subsequent *ad libitum* smoking session.

- **Aim 1.1**: Test the hypothesis that performance on the Hypothetical MPT will be significantly associated with performance on the Actual MPT.
- **Aim 1.2**: Test hypothesis that marijuana craving post-administration will be lower than craving assessed pre-administration.
- **Aim 1.3**: Test the hypothesis that marijuana puff topography from the *ad libitum* marijuana self-administration session will be related to self-reported grams of cannabis used per week.

B.2. SAMPLE DESCRIPTION AND RECRUITMENT

Participants will be recruited from the community via flyers, advertisements, and social media. Potential subjects will be screened via phone and staff will summarize study procedures. Eligible subjects will be scheduled for an initial laboratory visit. Preliminary data suggests that there is much variability in marijuana use practices; therefore, we will include individuals with a range of use practices and patterns to capitalize on variability. During the initial laboratory visit, participants will provide informed consent and will be enrolled in the study using the following inclusion criteria:

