
Drug: Marijuana (**5.9%** Δ^9 -tetrahydrocannabinol/THC) cigarettes will be provided by the NIDA Drug Supply Program. This dose was selected because administration of **5.9%** THC will closely model potency of marijuana obtained outside the laboratory as marijuana preparations have increased from 3.4% in 1993 to 8.8% in 2008 [10].

Laboratory Session 1: Controlled Paced Puff Smoking Procedure: Subjects will complete the Hypothetical (not associated with marijuana available to smoke) Marijuana Purchase Task (MPT), Actual MPT (identical to Hypothetical MPT but a response choice will be selected at random to determine amount of marijuana available to be smoked), and self-report measures of craving and subjective effects. A blood pressure cuff will be attached to continuously record heart rate (HR) and blood pressure (BP) during the entire experimental session for safety monitoring. Selection of marijuana amount available to smoke: A response choice corresponding to an item price will be randomly selected from the Actual MPT measure completed during the session. Subjects

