will draw a number and will be given a monetary budget based on the maximum price set on the MPT measure (\$20) for the marijuana smoking session. Once the response choice/price has been selected, the corresponding number of marijuana hits will be available to smoke, and the subject will receive any remaining money from the monetary budget (e.g., budget=\$20, item selected from Actual MPT =\$5/unit, subject reported he/she would purchase 3 units at this price, 3 units will be available during the smoking procedure, and subject will receive the remaining \$5 from the monetary budget). The controlled paced-puffing procedure [11] includes instructions to "light the cigarette" (30s), "get ready" (5s), "inhale" (5s), "hold smoke in lungs" (10s), and "exhale." The puffing sequence will continue until the subject chooses to cease smoking or the number of available units has been reached (i.e., 20 hits). Subjects are not required to smoke any marijuana as our intention is to assess the relationship between Actual MPT performance and real smoking in the laboratory. Subjects will be informed that the administration session will last 1-hour regardless of number of marijuana hits available. This methodology is based on established procedures that have been successfully used to assess demand for Hypothetical versus Actual alcohol [12]. No more than 20 hits total will be available during the session due to potential safety concerns (e.g., increases in HR which reliably occur [5], [13]).

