Security and Regulatory Aspects for Marijuana: Marijuana cigarettes will be provided by NIDA and will be stored frozen in an airtight container in a locked refrigerator safe located in a cement block room without windows and one door that is locked with code-protected card-key access at [name] on the 3rd floor. Only DEA designated individuals will have access to this room (located in the same building and floor as the location of marijuana administration). Thus, the cigarettes will remain secure at all times. [name] will retrieve a designated number of marijuana cigarettes prior to a scheduled experimental session, humidify them at room temperature for 24 hours before use (per NIDA's instructions) in the same cement block room, and transfer them directly to the laboratory following the start of the session.

Statistical Analysis Plan: The primary aim of this investigation is to confirm the validity of the Marijuana Purchase Task (MPT; primary outcome measure). A linear regression will be performed with marijuana hits purchased on the Actual MPT predicting marijuana hits actually purchased and smoked in the laboratory; baseline total individual income will be included as a covariate. The first secondary aim includes change in marijuana craving pre- and post-marijuana smoking during the experimental session (secondary outcome measure). A two-sided t-test will be conducted to compare craving pre- and post-marijuana smoking. The second secondary aim includes correlation between puffs on the topography device during *ad libitum* marijuana administration and self-reported grams of marijuana used per week (secondary outcome measure).

References

- [1] Office of National Drug Control Policy, "Marijuana Resource Center: State Laws Related to Marijuana | The White House." Accessed: Oct. 29, 2013. [Online]. Available: http://www.whitehouse.gov/ondcp/state-laws-related-to-marijuana
- [2] J. G. Murphy and J. MacKillop, "Relative reinforcing efficacy of alcohol among college student drinkers," *Exp. Clin. Psychopharmacol.*, vol. 14, no. 2, pp. 219–227, May 2006, doi: 10.1037/1064-1297.14.2.219.
- [3] J. J. Palamar, D. C. Ompad, and E. Petkova, "Correlates of intentions to use cannabis among US high school seniors in the case of cannabis legalization," *Int. J. Drug Policy*, Feb. 2014, doi: 10.1016/j.drugpo.2014.01.017.

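### If the primary regression's predictor is hits bought at the drawn price, purchases cap smoking, so a positive slope alone cannot validate the task

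*Combined protocol and SAP*

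**What the plan says.** The Statistical Analysis Plan gives the validity of the Marijuana Purchase Task (MPT) as the primary aim. The analysis is: "A linear regression will be performed with marijuana hits purchased on the Actual MPT predicting marijuana hits actually purchased and smoked in the laboratory", with baseline income as a covariate. For this regression it names no price level or MPT index, no null value for the slope, no significance level, no interval, no variance estimator and no measure of agreement.

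The procedure is set out under Aim 1 and Laboratory Session 1:

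- Each MPT item asks "how many hits of marijuana would you take if they cost" a given price. Under Aim 1, one of the subject's "response choices is selected at random to determine the amount of marijuana to be administered".
- "A response choice corresponding to an item price will be randomly selected from the Actual MPT measure completed during the session". The subject "will be given a monetary budget based on the maximum price set on the MPT measure" (USD 20).
- Once the price is drawn, "the corresponding number of marijuana hits will be available to smoke". In the worked example, 3 units are bought and 3 are available.
- "The puffing sequence will continue until the subject chooses to cease smoking or the number of available units has been reached". No more than 20 hits are available in total.
- "Subjects are not required to smoke any marijuana as our intention is to assess the relationship between Actual MPT performance and real smoking".

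**The concern.** If the predictor is the quantity at the drawn price, the procedure sets it as the ceiling on the outcome. Someone who bought 1 hit cannot smoke more than 1; someone who bought 15 may smoke up to 15. A positive slope can then arise even if purchases say nothing about how much a person wants to smoke. The study could report a highly significant slope as confirming the task when the ceiling largely produced it.

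A second, smaller matter follows from the same ceiling. The spread of hits smoked is zero for those who bought none and probably grows with the number bought. The ordinary least-squares (OLS) standard error assumes constant spread.

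**Working it through.** **Inputs.** From the documents: n = 85; USD 20 budget and maximum price; ceiling of 20 hits; prices of USD 0.25 and 0.50 (Aim 1) and USD 5 (Session 1 example); income covariate. Not in the documents, so assumed: the rest of the price list, demand, smoking behaviour, a two-sided 5% level, and slope = 0 as the default test. There is no sample-size calculation to reproduce. The one piece of arithmetic given, the budget example, reproduces: 20 − 3 × 5 = 5.

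**1. The bound.** Let X be hits bought at the drawn price and Y hits smoked. X hits are available and smoking is optional, so 0 ≤ Y ≤ X for everyone.

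**2. What the bound alone does.** Let S be the number a participant would smoke with no ceiling, independent of X. Then Y = min(X, S), and E[Y | X = x] = P(S ≥ 1) + … + P(S ≥ x). The x-th hit bought adds P(S ≥ x), which is never negative.

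- S Poisson with mean 4: the first hit adds 1 − e⁻⁴ = 0.98; the fifth adds 1 − e⁻⁴(1 + 4 + 8 + 10.67 + 10.67) = 0.37.
- S Poisson with mean 2: the first adds 1 − e⁻² = 0.86; the fifth adds 1 − e⁻²(1 + 2 + 2 + 1.33 + 0.67) = 0.05.

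The line rises steeply at low X and flattens at high X. Hence two exceptions: mostly high purchases, and a low wish to smoke.

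**3. Simulation.** 4,000 trials per cell; OLS of Y on X and an independent income variable; t with 82 df. S is an overdispersed count (Poisson with a gamma-distributed mean), independent of X.

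| Purchases (median hits) | Mean S = 8: slope, slope = 0 rejected | Mean S = 4: slope, slope = 0 rejected |
|---|---|---|
| Random price, USD 20 budget (2.5) | 0.45, 100% | 0.22, 99% |
| Low, geometric (2) | 0.59, 100% | 0.36, 100% |
| Even, 0–20 (10) | 0.36, 100% | 0.15, 88% |
| Mostly high (18) | 0.19, 17% | 0.05, 4% |

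With a plain Poisson limit of mean 4 or 8, four other assumed price lists and even purchases gave 94–100% with OLS and 88–100% with HC3 robust standard errors. With mean 2, OLS rejected in 29–99% and HC3 in 28–82%. Under another mostly-high distribution OLS rejected in 5–7%. The largest mostly-high figure was 30%, from rerunning the table's last row with a plain Poisson limit of mean 8.

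**4. The slope is not the fraction smoked.** With a personal limit (log-normal, median 8), the slope was 0.50–0.70 while the mean fraction of purchased hits smoked was 0.88–0.97.

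**5. The standard error.** If half smoke everything and half nothing, Var(Y | x) = x²/4: 0.25 at 1 hit, 4 at 4 hits, 100 at 20 hits. If instead everyone leaves 0 or 1 hit at random, the variance is 0.25 at every x ≥ 1 and OLS is nearly right (coverage 92–95%). If purchases must fit the budget, the most that can be bought is 20/5 = 4 hits at USD 5, 2 at USD 10 and 1 at USD 20, but the full 20 at USD 1 or less. Mostly low purchases are therefore plausible but not established. In the simulations of step 3, with binomial, beta-binomial and uniform smoking added:

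| Purchases | OLS SE ÷ true SD | OLS 95% CI coverage |
|---|---|---|
| Low (first two rows above) | 0.39–0.61 | 55–76% |
| Even, 0–20 | 0.92–1.05 | 92–96% |
| Mostly high | 1.10–1.30 | 97–99% |

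HC3 raised the low-purchase coverage to 89–93%. In wider runs with low or moderate demand, HC3 covered only 72–80% if 80% smoked all they bought and 45–54% if 95% did; the bootstrap covered 76–82% and 50–59%.

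**The case against.** **The predictor is not confirmed.** The outcome wording already contains the purchase, so a drawn-price predictor puts the same purchase on both sides. The contrast, and the protocol's reference to MPT performance, could also fit a task-level index. On that reading the exact bound disappears; with mean hits over prices as predictor, OLS coverage was 71–85% at low, 89–96% at moderate and 98–100% at high demand. This stands as a limit on scope. The drawn-price reading remains the more natural one, because only hits bought at the drawn price can be smoked. The note equating available units with 20 hits is ambiguous, but the 3-unit example supports a ceiling per subject.

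**No test of slope = 0 is written down.** True; it is inferred as the regression default. But the plan offers nothing else from which validity could be concluded.

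**An independent wish to smoke is not the same as an invalid task.** In runs with a Poisson limit of mean 8, 52–87% of purchasers smoked all they bought and the mean fraction smoked was 0.77–0.95. Many people consuming what they bought is arguably the correspondence sought. This is fair: the rejection rates are not false-validation rates. They show that the test cannot separate such correspondence from the ceiling, which is a reason to report the fraction directly.

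**Stronger readings.** A reader might infer that the ceiling guarantees significance. It does not: both exceptions above are real. A reader might also infer that the planned standard error is simply too small and the primary p-value unsound. The documents give neither the price list nor smoking behaviour, the error can run either way, and it seldom changes the verdict on slope = 0. It matters for an interval that the plan does not promise.

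**Conclusion.** The point holds, conditional on the drawn-price reading, and should be addressed; confidence is medium. On that reading a significant positive slope is weak evidence of validity. With a mean wish of 4 or 8 hits, the ceiling alone led to rejection in about 88–100% of simulated trials; with a mean of 2, in about 30–99%; with mostly high purchases, usually in about 5–17% (30% at most). These sizes rest on assumed prices, demand and smoking behaviour. The bound itself rests only on the protocol.

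The standard-error point is secondary: an ordinary interval for the slope would probably be too narrow if purchases are mostly low, about right if evenly spread and too wide if mostly high.

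**What to change.** State which quantity is the predictor. If it is the quantity at the drawn price, keep the linear regression with income and report beside it:

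- among those who purchased at least 1 hit, the income-adjusted mean fraction of purchased hits smoked (fractional-logit or quasi-binomial model, robust CI);
- in the same group, the share who smoked everything they bought (exact binomial CI);
- the number who purchased 0.

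Base the validity conclusion on these, and say that rejecting slope = 0 is not by itself evidence of validity. If a CI for the slope is reported, use HC3 or bootstrap standard errors.

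The cost is a short paragraph of SAP text and a little more analysis, with no new data. Downsides: zero purchasers (on average 0–18 of 85 under the assumed price lists) do not enter the fraction analysis. HC3 intervals averaged 1.4–4.1 times the OLS width with low or moderate demand (0.8 times with mostly high purchases), and HC3 and the bootstrap still under-cover if most participants smoke all they bought. The CI for the fraction covered 93–96%, but only 80–90% if about 95% smoke everything; the exact CI for the share covered 95–99%.

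### The primary regression does not name its Actual MPT predictor; on the natural reading that answer also caps hits smoked, so a positive slope alone cannot confirm validity

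*Combined protocol and SAP*

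**What the plan says.** The Statistical Analysis Plan paragraph in section B.3 opens with the purpose: "The primary aim of this investigation is to confirm the validity of the Marijuana Purchase Task". The single primary analysis is that a "linear regression will be performed with marijuana hits purchased on the Actual MPT predicting marijuana hits actually purchased and smoked in the laboratory", with baseline individual income as the only covariate. It names no MPT item or index, no alpha, and no result that would count as validity.

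The Laboratory Session 1 text in the same section describes how the amount is set:

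- The draw: "A response choice corresponding to an item price will be randomly selected from the Actual MPT measure completed during the session".
- The amount: "Once the response choice/price has been selected, the corresponding number of marijuana hits will be available to smoke".
- The worked example, at $5 per unit out of $20: "subject reported he/she would purchase 3 units at this price, 3 units will be available during the smoking procedure".
- The end of smoking: "The puffing sequence will continue until the subject chooses to cease smoking or the number of available units has been reached". Smoking less is allowed: "Subjects are not required to smoke any marijuana as our intention is to assess the relationship between Actual MPT performance and real smoking".
- The money: each subject "will be given a monetary budget based on the maximum price set on the MPT measure", which is $20.

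Aim 1.1 in section B.1 states a different validation hypothesis, that Hypothetical MPT performance is associated with Actual MPT performance. The Statistical Analysis Plan does not list that analysis.

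**The concern.** The MPT gives one answer per price, so hits purchased on the Actual MPT could mean the answer at the drawn price, the answer at the lowest price, or a summary over all prices. The first is the natural reading, because only that answer has a laboratory outcome attached to it. On that reading the predictor is also the ceiling on the outcome. Someone who bought 3 hits can smoke 0 to 3, and someone who bought none must smoke none. The two variables are tied by the procedure before any behaviour is observed.

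At stake is the meaning of the only primary analysis. A small p-value for the slope could be presented as confirmation of the measure when much of it comes from the ceiling.

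**Working it through.** **Inputs from the document.** 85 subjects (section B.3, Aim 1 Approach); a $20 budget, a 20-hit maximum and one random price draw (Laboratory Session 1); income as covariate (Statistical Analysis Plan).

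**Assumptions.** A two-sided 5% test, because no alpha is stated and two-sided is given only for the craving t-test. The price list, demand curves and desire for hits are also assumed. Answers are taken to stay within the budget, that is at most min(20, floor(20/price)). The budget and the example suggest this, but no rule states it.

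**The plan's own figure.** The worked example reproduces: 20 − 3 × 5 = $5 returned. The sample size has no stated derivation, so there is nothing to reproduce.

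**Step 1: the bound.** Let x be the answer at the drawn price, D the hits the subject would smoke without a limit, and y the hits smoked. Then y = min(D, x), so 0 ≤ y ≤ x, and x = 0 forces y = 0. This needs no assumption beyond the drawn-price reading.

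**Step 2: the expected slope when desire is unrelated to the MPT.** If D is independent of x, then E(y | x) = P(D ≥ 1) + … + P(D ≥ x). Every term is non-negative, so the mean cannot fall as x rises. For Poisson desire with mean 3, e⁻³ = 0.0498:

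- P(D ≥ 1) = 1 − 0.0498 = 0.950
- P(D ≥ 2) = 1 − 4 × 0.0498 = 0.801
- P(D ≥ 3) = 1 − 8.5 × 0.0498 = 0.577

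Mean hits smoked therefore rise from 0 to 0.95, 1.75 and 2.33 as hits purchased go from 0 to 1, 2 and 3, with no link between the MPT and desire.

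**Step 3: how often the slope is significantly positive.** One specified set-up has 16 prices from $0 to $20 drawn uniformly, 2,000 trials per row, and ordinary least squares of y on x and income. Answers either follow a demand curve (answer at zero price uniform on 1–20, exponential decay in price with median rate 0.15 and log-SD 0.6) or are pure noise within the budget. D is independent of all answers. Each cell gives demand-curve answers, then noise answers.

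| Desire D | Drawn-price predictor: significant | Mean slope | Total over prices: significant | D not capped: significant |
|---|---|---|---|---|
| Poisson, mean 3 | 99%, 100% | 0.15, 0.17 | 79%, 10% | 3%, 3% |
| Poisson, mean 5 | 100%, 100% | 0.31, 0.30 | 98%, 16% | 2%, 3% |
| Poisson, mean 10 | 100%, 100% | 0.66, 0.64 | 100%, 27% | 3%, 3% |
| Half want none, rest 1–20 | 97%, 99% | 0.31, 0.31 | 63%, 10% | 3%, 3% |
| 80% want none, rest 1–20 | 58%, 67% | 0.13, 0.12 | 18%, 5% | 3%, 4% |

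Other assumed price lists and demand curves gave about 87–100% at a mean desire of 3 or more hits and 25–91% at 1 hit for the drawn-price predictor, against 2–5% without the cap. A whole-curve predictor gave about 16–72% at means of 3 to 10. The table shows that this last range depends heavily on the assumed answers. Coupling is weaker with a whole-curve predictor but is not reliably removed.

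**Step 4: what an uncapped correlation could detect.** By Fisher's z, the correlation detectable with 80% power is tanh((1.960 + 0.842)/√(85 − 3)) = 0.30. Power at r = 0.30 is 80% with 85 completers, 75% with 75 and 68% with 65.

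**The case against.** The strongest reply is that the regression answers the question the protocol poses. Subjects may smoke less than they bought, and Session 1 states its interest as the relation between Actual MPT performance and real smoking. Whether people smoke what they paid for is a fair part of that. This stands. In simulations where each purchased hit is smoked with a fixed probability, the central 95% range of the slope was 0.47–0.73 at 60% follow-through and 0.89–1.00 at 95%. With between-person spread the ranges were 0.35–0.83 and 0.79–1.01. The regression should be kept, and a reader who infers that it is empty goes too far.

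A reader might also infer that the plan will declare an uninformative task valid. The documents do not say so: they state no test against zero and no success rule. Slope versus zero is the default reading, not a written one.

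Nor does the test give the same answer whatever people want. The effect is much weaker when desire is low, and the documents give no level of desire.

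Reading the outcome as hits purchased, which would fix the slope at 1, is strained, because the text says purchased and smoked.

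The parenthetical 20 hits in the stopping rule could suggest a common limit for everyone, which would remove the cap. The 3-unit example contradicts that, and the two should be reconciled.

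**Conclusion.** The point holds and should be fixed. Two parts rest on the text alone: the predictor is not identified, and on the drawn-price reading hits smoked lie between zero and the predictor for every subject. The third part, that a significantly positive slope is likely without any link between the MPT and desire, needs the inferred slope-versus-zero reading and the assumptions listed above. Its size is about 87–100% at a mean desire of 3 or more hits and 25–91% at 1 hit, against 2–5% uncapped. These figures show the mechanism and do not predict this trial's result.

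The defect is an undefined predictor and a missing basis for interpretation. It is not a wrong model. It might seem to follow that a pass margin is needed, but the documents give no basis for choosing one. At an illustrative margin of 0.80, requiring both the slope and the proportion smoked to clear it would still pass up to 44% of trials at mean desire 10 with desire unrelated to the MPT.

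**What to change.** 1. State that the predictor is the Actual MPT answer at the drawn price and that the outcome is hits smoked.
2. Keep the planned regression with income, but do not treat a slope above zero as validation. Report the slope with its 95% confidence interval. Also report the proportion of purchased hits smoked among those with at least one hit available, with its interval, the number who stopped before their limit, and zero purchasers separately. No pass margin is required.
3. Limit the conclusion from this analysis to follow-through on purchases.
4. For validity evidence not capped by the draw, add two analyses of data the protocol already collects. The first is the Spearman correlation of one pre-specified Actual MPT index (for example, hits at the lowest price) with Session 2 ad libitum puffs, which the plan now uses only against self-reported grams. The second is the Hypothetical-versus-Actual association of Aim 1.1. If the data have already been analysed, label both as post hoc.

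**Cost.** No new data, but two small extra analyses and a headline less favourable than a small p-value. The Session 2 correlation links measures from different sessions. It has about 80% power only for r of about 0.30 or more with 85 completers, and less with ties and the two-joint limit.

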Laboratory Session 2. *Ad Libitum* Smoking Topography Procedure: Participants will complete baseline measures including the Hypothetical MPT, and will then complete a 1-hour *ad libitum* marijuana self-administration session for assessment of smoking topography. Marijuana cigarettes (5.9% THC) will be smoked through a handheld smoking topography device (CReSSMicroTM). The device will include a holder for the cigarette and study staff will place the cigarette in the device. The subject will light the cigarette and each puff will register immediately upon inhalation. Data from the device will be downloaded and indices of topography will be recorded including number of cigarettes, number of puffs, puff volume (ml), puff duration (ms), average puff velocity (ml/s), and time to peak velocity (ms). Logs will also be maintained by the PI and RA documenting number of puffs smoked and each cigarette or partial cigarette smoked ensuring an accurate count of marijuana cigarettes smoked during the session. These procedures have been successfully used to assess marijuana smoking topography [14]. A maximum of two joints will be available during the session.

Sobriety Assessment: Subjects will receive snacks upon the completion of the administration session. Subjects will remain in the laboratory for 3-hours following the smoking procedure (psychotropic effects of smoked marijuana taper off within 2-3 hours [15]), and will subsequently be evaluated for motor signs of intoxication. Following completion of a field sobriety test [16], subjects will be transported home in a taxi.

Compensation: Participants will be paid \$20 for the baseline session, \$10 for the physical exam, and \$50 for each experimental session (and amount remaining from \$20 tab) for a total of at least \$130 and up to \$150.

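### Does the primary regression need a written rule for Actual MPT answers above the $20 budget or the 20-hit maximum?

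*Combined protocol and SAP*

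**What the plan says.** In B.3, Laboratory Session 1, one Actual MPT price is drawn at random and the subject "will be given a monetary budget based on the maximum price set on the MPT measure", which is $20. Then "the corresponding number of marijuana hits will be available to smoke, and the subject will receive any remaining money from the monetary budget". The worked example uses $5 per unit: "subject reported he/she would purchase 3 units at this price, 3 units will be available during the smoking procedure", and $5 is returned. A second limit follows: "No more than 20 hits total will be available during the session due to potential safety concerns". Smoking is optional, because "our intention is to assess the relationship between Actual MPT performance and real smoking in the laboratory".

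The Compensation paragraph pays $50 "for each experimental session (and amount remaining from" a $20 tab, for a total of $130 to $150.

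The Statistical Analysis Plan gives one analysis for the primary aim, a linear regression with "marijuana hits purchased on the Actual MPT predicting marijuana hits actually purchased and smoked in the laboratory". On adjustment, it adds only that "baseline total individual income will be included as a covariate". It has no sentence on answers above either limit. The Actual MPT is described as identical to the Hypothetical MPT apart from the random draw, and no ceiling on answers is stated. The form and its price list are not in the documents.

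**The concern.** Purchasing appears on both sides of the regression. At the drawn price there are three quantities: the answer r, the hits made available a, and the hits smoked s. Inside both limits r = a. Above a limit r exceeds a, and the choice of predictor matters.

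With r as predictor, the shortfall r − s mixes a part imposed by the limit (r − a) with a part the subject chose (a − s). With a as predictor only the chosen part remains, but over-stated purchasing disappears from view. This is the only analysis of the primary aim, so an undefined predictor could allow the choice to be made after the data are seen.

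Two further silences add to the worry. The worked example lies inside the budget, so it does not show what happens when price times answer exceeds $20. And each subject answers at many prices, yet the analysis sentence does not say that the predictor is the answer at the drawn price.

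**Working it through.** **The plan's own figures.** Worked example: 20 − 3 × 5 = $5, as stated. Compensation: 20 + 10 + 2 × 50 = $130, and 130 + 20 = $150, as stated. The refund therefore lies between $0 and $20. That range does not fix how many hits an over-budget answer delivers.

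**Where the limits fall.** Reading the budget as a spending ceiling (an assumption made only for this check), the limit is min(20, floor(20/price)). At the prices printed in the documents:

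| Price | floor(20/price) | Limit | Which binds |
|---|---|---|---|
| $0.25 | 80 | 20 | session maximum |
| $0.50 | 40 | 20 | session maximum |
| $5 | 4 | 4 | budget |
| $20 | 1 | 1 | budget |

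Over-limit answers are therefore arithmetically possible. For example, a subject who answers 10 at $5 and smokes 3 has r − s = 7, of which r − a = 6 is the limit and a − s = 1 is choice.

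**Possible effect on the estimate.** Assume a $5 price (limit 4), answers spread evenly over 0 to K, every available hit smoked, and income left out. The slope of s = min(r, 4) on r is Sxy/Sxx, and t at n = 85 is √(83·R²/(1 − R²)).

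| K | Share above limit | Slope on r | R² | t |
|---|---|---|---|---|
| 4 | 0/5 = 0% | 1.00 | 1.00 | – |
| 5 | 1/6 = 17% | 15/17.5 = 0.86 | 0.96 | 47.3 |
| 6 | 2/7 = 29% | 20/28 = 0.71 | 0.91 | 28.8 |
| 8 | 4/9 = 44% | 30/60 = 0.50 | 0.79 | 17.9 |
| 10 | 6/11 = 55% | 40/110 = 0.36 | 0.70 | 13.8 |

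The slope on a is 1.00 in every row. That is an identity: assuming every available hit is smoked makes s equal to a. It is not evidence that a is the better predictor. The spread of answers and the values of K are also assumptions.

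**Harsher assumptions.** A simulation with n = 85 used 11 assumed prices from $0.25 to $20, median zero-price demand of 8, 15 or 25 hits, two assumed price sensitivities, and 90% of available hits smoked. Over-budget answers made up about 23% to 78% of draws. With delivery cut to both limits, R² on the raw answer was 0.16 to 0.75, and on hits available 0.97 to 0.98. At the lowest value, t = √(83 × 0.164/0.836) = 4.0. If an over-budget answer is assumed to deliver nothing, R² on the raw answer was 0.01 to 0.40, and at the lowest value t = √(83 × 0.014/0.986) = 1.1.

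**What the wording supports.** The worked example describes the MPT answer as what the subject reported he or she would buy. The analysis sentence contrasts hits bought on the task with hits actually bought and smoked in the laboratory. The stated intention is to relate Actual MPT performance to real smoking. All three point to the task answer as predictor and laboratory behaviour as outcome. Each subject has one drawn price and hence one smoking outcome, so the matching answer is the one at that price.

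**Refund above 20 hits.** For 30 hits at $0.25 the refund is 20 − 7.50 = $12.50 if charged on the request, or 20 − 5.00 = $15.00 if charged on 20 delivered. Neither figure enters any analysis.

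**The case for a change.** The strongest case for a change is that a lean in the wording is not a definition. The slope and R² carry the validity claim, and they can move a great deal with the choice of predictor. Under the most severe delivery assumption even the test on the raw answer could fail. Naming the predictor in advance would cost one sentence.

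Part of this stands. The documents do not state what an over-budget answer delivers, nothing elsewhere in them supplies it, and the drawn-price qualifier is left to inference.

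The rest is weaker. The two predictors are not equal rivals. Hits available are already cut by the limits and bound hits smoked from above, so a close fit on them is partly built in. For an aim of validating the task, the task answer is the sensible choice, and the wording already favours it. The large effects come from invented demand curves, an invented price list and, in the worst case, a delivery rule that the documents do not state. That worst case comes from how the session is run, and defining the predictor as the task answer would not alter it.

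**Conclusion.** No change to the plan follows. This is missing detail that an analyst would fill sensibly: the predictor is the Actual MPT answer at the drawn price, and the outcome is hits smoked. No stated rule gives a wrong result.

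The effect on the result is nil if no drawn answer exceeds a limit. Otherwise its size cannot be determined from the documents. In the $5 illustration it changes the slope and R² but leaves a clear association, with t at least 13.8. That reassurance does not cover every delivery assumption.

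The conclusion rests on two things: the plain reading of the analysis sentence, and the fact that the share of over-limit answers is unknown and may be governed by an MPT form outside these documents. What an over-budget answer delivers is for the sponsor to state, and no rule is suggested here. The refund above 20 hits has no statistical consequence.
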